5. STATISTICAL / ANALYTICAL ISSUES

Visit windows

In accordance with the protocol, due to the non-interventional study design it's not possible to appoint exact times for the study visits, although it is expected that the period of observation will be approximately 6 months. The frequency of the visits will be assigned by each physician according to their routine practice. It is anticipated that the patients will visit their physician every 3 months and more often at the beginning until the patient achieves target blood pressure.

So, for the analysis and summary of clinical laboratory, efficacy, and safety data in case of this analysis/summary performed on "by visit" base. In the event of multiple values for an assessment within an analysis window, the value closest to the scheduled visit date will be used for analyses. If two values tie as closest to the time point (for example, one value is before and the other value is after the time point), then the later value will be selected as the analysis value.

Analysis Window	Start	End	Target Asses dupli	sment to be used if cates	
Baseline visi	t <1		NA		
Month 1 Month 3 Month 6	2 46 136	45 135 NA	30 90 Closes 180 equidi	st to target day, if stant use later result.	

The definition for the study days included in each study window is defined as below:

Treatment Day prior to first dose = Visit Date – Date of First Dose

Treatment Day on or after first dose = Visit Date – Date of First Dose + 1

Adjustments for Covariates

No specific adjustments for covariates will be made in all statistical analyses, unless specified otherwise per-analysis level.

Handling of Dropouts or Missing Data

Missing efficacy outcomes will be assumed to be missing at random (MAR) and thus will not be imputed in the primary analysis. However, if greater than 1% of all primary/secondary outcomes that should be available for analysis are missing, a sensitivity analysis will be undertaken in addition to the primary MAR analysis.

Confidential

This sensitivity analysis will include an evaluation of the results of models developed under the assumptions of:

1) last observation carried forward;

2) worst extreme case imputation and;

3) regression model imputation using all available information.

Outlier identification

During data Quality Control outlier identification will be performed using adjusted Z-score method (Iglewicz and Hoaglin, 1993).

$$M_i = \frac{0.6745(x_i - \tilde{x})}{MAD}$$

where MAD – median absolute deviation, x - median.

Values with Z-score > 3.5 will be considered outliers for study variables considered normally distributed. Preliminary normality test (Shapiro–Wilk criterion) will be performed for these variables. In case if normality distribution hypothesis will be rejected based on Shapiro–Wilk test results, median and IQR (interquartile range) will be used for outlier identification. Values > 1.5 IQR far from median value will be considered outliers. No data will be excluded / modified based on outlier identification, however, additional medical context assessment for these data will be performed and data quality control / source verification check will be considered.

Data Monitoring

Data quality monitoring, including safety data review and reconciliation, will be implemented periodically by the Data Manager from a Contract Research Organization (CRO). Details will be described in the Data Management Plan.

Multiple Comparisons/Multiplicity

When needed, corrections for multiplicity will be justified and performed according to Bonferroni. Overall alpha-level will be controlled and will not exceed 0.05

The interim analysis will not be taken into account within multiplicity adjustment procedure.

Examination of Subgroups

Primary and some secondary and exploratory endpoints will be analyzed in subgroups of patients: overweight, obese (stages I-III), impaired glucose tolerance (yes, no), metabolic syndrome (yes, no), diabetes mellitus (yes, no) etc (see "EFFICACY ANALYSES" chapter).

This analysis may be limited for the Republic of Kazakhstan sample as this sample has limited sample size. This will be noted in the statistical analysis report accordingly.

6. STUDY POPULATION CHARACTERISTICS Patient Disposition

Data regarding how many patients reached the various stages of the trial, how many dropped out, discontinued the treatment and for what reasons (death, ADRs, treatment failure, withdrew consent, lost to follow-up) will be presented for each subgroup and for study in bulk. Standard diagram describing study patient flow will be provided.

7. DEMOGRAPHICS AND OTHER BASELINE CHARACTERISTICS Demographics

All demographic and other Baseline characteristics will be summarized for overall analysis population as well as for subgroups of patients listed in the section 9.3 of the document

Medical History, Concurrent Medical Conditions and comorbidities

Medical history is history of diseases indicated before signing of the Informed Consent Form.

Concurrent medical conditions are those significant ongoing conditions or diseases that are present at signing of informed consent.

Comorbidities (concomitant disease) are diseases which occur after start of Edarbi[®] treatment and are not related to the Edarbi[®] treatment. Comorbidities may include not limited to cardiovascular disorders (coronary artery disease, peripheral artery disease, cerebrovascular disease), diabetes, chronic pulmonary artery disease, chronic kidney disease. The condition (ie, diagnosis) should be described.

Risk factors are conditions which increase probability of cardiovascular disease in patients with HTN at the moment of signing ICF. Risk factors are described in accordance with Russian guidelines "Diagnostics and treatment of hypertension" (2010).

Time of medical event/disease	How it should be documented
Birth to day before ICF signed	Medical history
At the moment of ICF signing	Risk factors
At the moment of ICF signing	Concurrent medical conditions
After ICF signing and start of Edarbi® treatment	Adverse Events

Page 18/31

After coding, medical history, risk factors, concurrent medical conditions and adverse events will be summarized and reported in accordance with denoted conventions (see. "Summary of study data").

Treatments to be documented in the study

All medications recorded in accordance with study protocol, including:

- Prior HTN treatment
- HTN treatment received during follow-up
- Concomitant medication

- will be summarized using denoted descriptive statistics (see "Summary of study data"). Number of subjects with these treatments will be summarized.

Edarbi® treatments will be registered in the CRF The following information about Edarbi® treatment will be collected:

- start date of Edarbi®,
- end date of Edarbi® treatment or prolongation of Edarbi® treatment,
- single and total dose, dose regimen,
- reason(s) for discontinuation of Edarbi ® treatment (if applicable).

Edarbi® should be administered according to the official prescribing information (The Russian SmPC). The starting dosage will be 40 mg per day. In case of insufficient efficacy, the dosage could be increased up to 80 mg per day.

HTN treatment

In case of combination HTN-treatment all co-medications for HTN treatment should be registered in Case Report Form. For every type of co-medication following data should be documented:

- INN, trade name,
- dosage regimen (dose taken),
- duration of treatment.

Prior HTN treatment

Medication taken before start of the study is called prior medication. In case the patient already underwent HTN treatment during 12 weeks prior to start of Edarbi® treatment, details of the therapy should be recorded in the CRF.

Concomitant medication

Concomitant medication is any drug given in addition to the HTN treatment. These drugs may be prescribed by a physician or obtained by the patient over the counter. Concomitant medication is not provided by the sponsor.

The information about concomitant medication can be received both on base of medical records and on questions to patients (according to routine practice). During the visits the information about changes in the concomitant therapy is recorded. At each study visit, patients will be asked whether they have taken any medication other than the study medication (used from signing of informed consent through the end of the study).

All drugs and drug combination for concomitant medication will be registered in CRF. For every type of drug there will be documented trade name, INN, dosage regimen (dose taken), duration of treatment, indications.

The area of interest is on antidyslipidemic and antidiabetic drugs.

Follow-up HTN treatment

If a patient withdraws from study due to change of Edarbi® treatment, the follow-up prescribed HTN treatment should be documented in the CRF.

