9.4.5 Discontinuation/withdrawal of patients from the study

9.4.5.1. Criteria for Discontinuation or Withdrawal of a patient

Patients may be discontinued from study or study drug at any time, at the discretion of the investigator. Specific reasons for discontinuing a patient from the study are:

1. Voluntary withdrawal of informed consent in patient's request or at the request of patient's legally acceptable representative.

The patient (or patient's legally acceptable representative) wishes to withdraw from the study. The reason for withdrawal, if provided, should be recorded in the CRF. Note: All attempts should be made to determine the underlying reason for the withdrawal and, where possible, the primary underlying reason should be recorded (ie, withdrawal due to an AE or lack of efficacy should not be recorded in the "voluntary withdrawal" category).

2. Development of exclusion criteria or other safety reasons (not a AE or SAE) during the study.
3. Adverse Events (AE)/ Serious Adverse Events (SAE), including Patient's death

The patient has experienced an AE or SAE that requires early termination because patient is unwilling to continue because of the AE or SAE or continuation of patients' visit to the clinic is impossible or any other occurrence which can be happened.

4. Protocol deviations, incorrect enrolment of the patient. The investigator and the sponsor will decide whether there is a deviation from the protocol.
5. Lost for observation within the framework of the study. The patient did not return to the clinic and attempts to contact the patient were unsuccessful.
6. Study termination. Sponsor decision or regulatory authorities' requirement about cessation of the study.
7. Pregnancy. The patient is found to be pregnant.

Note: If the patient is found to be pregnant, the patient must be withdrawn immediately.

8. Other (specify)

If the patient is lost for observation within the framework of the study that is, it is impossible to conduct the final visit; the investigator must do its best to get in touch with the patients for getting full information and clarifying the reasons of the loss of contact. Premature end of HTN treatment by Edarbi® automatically means end of data collection.

Details for the premature termination of the study/sites as a whole are provided in section 9.6 (Premature termination or Suspension of Study or Investigational Site).

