13.2.2. Statistical analysis methods

Primary study outcome – change from baseline in clinic SBP value tot Visit 4 will be estimated with 95% confidence interval construction.

In addition, clinic SBP (DBP) change from baseline will be assessed and evaluated using Mixed model repeated measures (MMRM) methodology [30, 31]. The multiple visits for each patient will be incorporated as repeated measures within each patient. Visit will be treated as a categorical predictor and baseline SBP (DBP) will be included as a covariate. An appropriate covariance structure will be selected to provide estimates (Least Square Means) of change from Baseline and to perform statistical analysis at Visit 4. The dose-response trend hypothesis test will be conducted using the appropriate contrast statement for a linear (ordinal dose) trend. In addition, Least Squares Means, the associated standard errors and 95% confidence intervals will be displayed by each individual dose group.

Patients who reached target level of SBP (DBP) at visits 2, 3 and 4 will be presented using frequencies and percentages for the study population. Patients who respond to therapy at visits 2, 3 and 4 will also be presented using frequencies and percentages. Secondary and exploratory outcomes will be analysed using descriptive statistics and frequencies and percentages as follows:

- Changes in systolic BP (SBP) during the treatment with Edarbi® (V2-V3) will be calculated and presented in summary tables using descriptive statistics for continuous variables;
- Changes in diastolic BP (DBP) during the treatment with Edarbi® (V2, V3) will be calculated and presented in summary tables using descriptive statistics for continuous variables;
- Percentage of patients who achieve target SBP<140 mm Hg (V2, V3, V4) will be described and presented in summary tables using absolute frequencies and percentages as well as 95% confidence intervals,
- Percentage of patients who achieve target DBP<90 mm Hg (V2, V3, V4) will be described and presented in summary tables using absolute frequencies and percentages as well as 95% confidence intervals;
- Percentage of patients who respond to Edarbi® therapy (defined as decrease of SBP \geq 20 mm Hg or decrease of DBP \geq 10 mm Hg; V2, V3, V4) will be described and presented in summary tables using absolute frequencies and percentages as well as 95% confidence intervals;

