9. EFFICACY ANALYSES

The primary, secondary, and exploratory efficacy analysis will be performed in two sets of data:

- 1) Full Analysis Set (defined as enrolled subjects who tookat least one dose of study drug)
- Per protocol analysis set (defined as subjects who took at least one dose of study drug and having all inclusion and no exclusion criteria)

For performing interim analysis data of first 470 enrolled patients will be used for the efficacy analyses listed in this section. For the interim efficacy analyses applicable methodology listed in this section is planned to be used. The interim analysis will be performed on the base of full analysis set.

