9.1. Statistical Analysis of the Primary Efficacy Variable(s)

Primary study outcome – change from baseline in clinic SBP value to Visit 4 will be estimated with 95% confidence interval construction and analyzed with paired t-test in pairwise comparison with baseline SBP

Changes in systolic BP (SBP) during the treatment with Edarbi[®] will be evaluated from baseline to Month 1,3 and 6. Additionally the changes of SBP from baseline to mentioned visits will be analyzed with paired T-test in pairwise comparisons with baseline level of the variable.

In addition, clinic SBP (DBP) change from baseline will be assessed and evaluated using Mixed model repeated measures (MMRM) methodology. The multiple visits for each patient will be incorporated as repeated measures within each patient. Visit will be treated as a categorical predictor and baseline SBP (DBP) will be included as a covariate. An appropriate covariance structure will be selected to provide estimates (Least Square Means) of change from Baseline and to perform statistical analysis at Visit 4 (Month 6). In addition, Least Squares Means, the associated standard errors and 95% confidence intervals will be displayed by each individual dose group (in case if exposition assessment will reveal distinct dose groups, then group factor and group * visit interaction will be added to the model).

Patients who reached target level of SBP (DBP) at visits 2, 3 and 4 will be presented using frequencies and percentages for the study population.

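### SAP 5 calls the primary result a MAR analysis, but SAP 9.1 makes it an unimputed paired change that uses only patients with a Month 6 BP; the MMRM that MAR supports is only additional

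*SAP*

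**What the plan says.** - **Missing data (SAP 5, Handling of Dropouts or Missing Data).** The rule reads: "Missing efficacy outcomes will be assumed to be missing at random (MAR) and thus will not be imputed in the primary analysis". If more than 1% of the primary and secondary outcomes are missing, "a sensitivity analysis will be undertaken in addition to the primary MAR analysis". The added runs are last observation carried forward (LOCF), worst-case imputation and regression imputation.
- **Primary estimate (SAP 9.1).** The "change from baseline in clinic SBP value to Visit 4 will be estimated with 95% confidence interval construction and analyzed with paired t-test". Protocol 13.2.2 has the same order without the t-test: "change from baseline in clinic SBP value tot Visit 4 will be estimated with 95% confidence interval construction".
- **Role of the MMRM (SAP 9.1).** "In addition, clinic SBP (DBP) change from baseline will be assessed and evaluated using Mixed model repeated measures (MMRM) methodology". Visit is a factor and baseline a covariate. The covariance structure is left to be chosen, and no baseline value is named for the least-squares (LS) mean.
- **Analysis set (SAP 9).** The Full Analysis Set (FAS) is everyone enrolled who took at least one dose. There is no condition on having a Month 6 reading.
- **Visit windows (SAP 5).** Month 6 opens on day 136.
- **Rates (SAP 3).** Percentages use the non-missing denominator.
- **Early leavers.** Protocol 13.2.4 says their last BP will be collected and they will not be dropped from the efficacy analysis. Protocol 13.2.5.1 plans no imputation. Protocol 9.4.5.1 ends data collection when Edarbi is stopped.
- **Scope (SAP 2.4 and 4).** This SAP covers the Kazakhstan patients only, with no sample size calculation of its own.

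**The concern.** The SAP uses MAR as its reason for not imputing. That reasoning fits a likelihood model that uses the Month 1 and Month 3 readings of patients who later leave. It does not fit a paired mean, which discards those patients. The SAP does not state the restriction to patients with a Month 6 reading, but it follows from a paired analysis without imputation.

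The documents foresee leaving that is related to blood pressure. SAP 6 (Patient Disposition) lists treatment failure among the reasons for stopping. Protocol 9.4.5.1 separates such cases from voluntary withdrawal: "withdrawal due to an AE or lack of efficacy should not be recorded" under that category.

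At stake is what the headline describes. The main SBP result and the response and target rates would describe patients still measured at about six months, while the label suggests an estimate for the whole FAS that is valid under MAR.

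**Working it through.** **1. The plan's own figures (protocol 13.4).** Inputs: SD 17.79, correlation 0.4375, mean change -17.311, 95% CI half-width 1 mm Hg with probability 0.9, dropout 25%.

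- SD of change = 17.79 × √(2 × (1 − 0.4375)) = 18.87.
- The exact conditional calculation gives 1437 pairs (probability 0.9027; the protocol states 0.903).
- 1437 / 0.75 = 1916. Both figures reproduce.
- The plan therefore expects 1916 − 1437 = 479 patients without a pair. That is 25%, far above the 1% trigger.

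**2. Size of the bias in general.** Completer mean minus overall mean = d × (completer mean − dropout mean), where d is the dropout fraction. At d = 0.25, a gap of 2, 4 or 8 mm Hg between the groups moves the paired mean by 0.5, 1.0 or 2.0 mm Hg.

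**3. Precision for comparison.** Half-width = t × 18.87 / √n.

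- Whole study, 1437 pairs: 0.98.
- Kazakhstan enrolment is not given. Assuming it is proportional to sites, 1916 × 10/90 ≈ 213 enrolled and 0.75 × 213 ≈ 160 pairs, so the half-width is about 2.9.

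**4. Assumed dropout scenarios at 25%.** Simulations used the protocol's SD, baseline correlation and mean change. Correlations between follow-up visits of 0.4375 to 0.75 are assumed. All rows except the last also assume 213 patients, baseline SBP 155 and dropout after Month 1 or Month 3. The last row comes from a separate run of 1,000,000 patients. Negative bias means the fall is overstated.

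| Assumed driver of leaving | Paired bias, mm Hg | Coverage of paired 95% CI |
|---|---|---|
| Random | -0.02 to -0.05 | 95-96% |
| Recorded SBP ≥140, half of dropout | -0.02 to -0.74 | 92-95% |
| Recorded SBP ≥140, all dropout | -0.01 to -1.39 | 84-95% |
| Fall under 10, half of dropout | -1.49 to -2.33 | 64-83% |
| Fall under 10, all dropout (extreme) | -2.80 to -4.41 | 14-52% |
| Recorded SBP <130 | -0.06 to +2.04 | 73-96% |
| High baseline SBP, odds ratio 1.5 to 3 per SD | +0.96 to +2.29 | not run |

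A more extreme baseline-driven case gave +3.3. An MMRM with unstructured covariance and the LS mean at the FAS mean baseline stayed within 0.1 mm Hg in the first six rows. A likelihood estimate using baseline and Month 3 stayed within 0.02 in the last. This is expected, because the data were generated as MAR. Under random dropout the root mean squared error is 1.4 for the MMRM and 1.5 for the paired mean.

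**5. Where the MMRM does not help.** If patients leave because of an SBP ≥140 that is never recorded, the bias at follow-up correlations 0.4375, 0.6 and 0.75 is -1.36, -1.78 and -2.16 for the paired mean. It is -2.12, -1.85 and -1.37 for the MMRM. Neither is uniformly better.

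**6. Confidence interval of the LS mean.** The LS mean is conditional on the observed mean baseline. A simple check ignores the information from Months 1 and 3:

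- Residual SD = 17.79 × √(1 − 0.4375²) = 16.00; 16.00 / √160 = 1.265.
- Baseline part = (1 − 0.4375) × 17.79 = 10.01; 10.01 / √213 = 0.686.
- Total SE = √(1.265² + 0.686²) = 1.439.
- Half-width is 1.975 × 1.265 = 2.5 without the baseline part and 1.975 × 1.439 = 2.8 with it.
- The narrower interval covers the population mean change about 92% of the time. The simulations gave 90-93%, and about 95-97% once the baseline variance was added.

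**7. Rates, same scenarios.** The completers' SBP <140 rate is 2 to 8 points too high if patients with SBP ≥140 leave and 7 to 12 too low if patients with SBP <130 leave. Counting missing as not achieved is 3 to 23 points too low across the target and response rates, so it is a bound and not an estimate.

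**The case against.** Much of this is already handled. At 25% dropout the 1% trigger would almost certainly fire. The MMRM sits inside the primary-variable section, and SAP 11 requires its LS means, standard errors and 95% CIs. Reasons for dropout are tabulated. A reader might infer that the plan ignores dropout; it does not. What remains is which number leads and how it is labelled.

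The outcome is defined as change on Edarbi therapy, so the change in patients still treated and measured is a legitimate descriptive target. That is true, provided it is labelled so. The MMRM answers a different, hypothetical question, and the documents do not choose between them.

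The swap has its own flaws. The SAP fixes neither the covariance nor the baseline at which the LS mean is taken. Using the observation-weighted mean baseline would shift the result by 0.2 to 0.8 mm Hg in the non-random scenarios of the first six rows. The unadjusted interval also covers less well than the paired one under random dropout. These points stand, and the fix has to meet them.

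The Kazakhstan analysis was not originally planned or powered, and its assumed half-width of about 2.9 mm Hg makes a bias of 0 to 1.5 less prominent. That lowers the severity but does not make the label right.

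**Conclusion.** The concern holds as a mismatch between a stated assumption and the estimator it is attached to. MAR does not make a complete-pair mean unbiased; that needs missingness unrelated to the change. The planned safeguards reduce the consequences without correcting the headline or its label. Severity is minor to should-fix.

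Two stronger readings are not supported. A reader might infer that the bias favours the drug. The documents give no dropout mechanism, and leaving driven by high baseline SBP or by low follow-up SBP can understate the fall. A reader might also infer that SAP 9.1 breaks the promise in protocol 13.2.4. That section does not say an early leaver's last BP must enter the paired Month 6 estimate; by-visit tables, the MMRM and the LOCF run could satisfy it. The texts still need to be reconciled.

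The scenario sizes rest on the protocol's 25% whole-study dropout, equal SDs across visits, and assumed mechanisms, follow-up correlations, baseline SBP and Kazakhstan enrolment.

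**What to change.** 1. **SAP 9.1 and 5.** Present the Month 6 MMRM change as the MAR-based primary estimate for the FAS, side by side with the protocol-defined paired change. Label the paired change as patients with a Month 6 BP and stop calling it a MAR analysis.
   - Specify unstructured covariance, and take the LS mean at the mean baseline of all FAS patients, not the observation-weighted mean.
   - Include the variance of the baseline mean in the CI, or model baseline as a response.
   - State that the MMRM estimates the change as if all patients had stayed on treatment and been observed to Month 6, that it omits patients with no post-baseline BP, and that it does not cover leaving driven by unrecorded BP. Keep the sensitivity runs for that reason.
2. **Rates.** Also show response and target-BP rates on the full FAS with missing counted as not achieved, as the planned worst-case run, labelled a conservative bound.
3. **Reconcile** protocol 13.2.4 (early leavers kept in efficacy) and 13.2.5.1 (no imputation) with SAP 5 and 9.1.

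The cost is SAP wording, aligned protocol text and a few tables; the planned sample size does not change. The headline may be slightly less favourable, and the country result must be shown both ways to stay comparable with the whole study.
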